Participants will undergo surgery using TME 15 weeks (\pm 14 days) after start of RT according to a standardized technique, unless there are contraindications for surgery ([Ridgway 2003](#), [Parfitt 2007](#)), if the participant refuses, or if the participant has a cCR and is eligible for organ preservation.

The choice of the surgical procedure, abdominoperineal resection or low anterior resection, is at the surgeon's discretion. Further details will be described in a dedicated surgical charter.

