8.1.2 Tumor Evaluation Methods and Response Assessment

Rectal cancer staging, and measurement at baseline and after chemoradiation should be performed as per NCCN Guidelines for Patients Rectal Cancer 2019. For participants who received induction treatment the baseline assessments will be based on MRI, endoscopy and DRE and biopsy, if required. For participants without induction treatment, the baseline assessment will consist of MRI only. For all participants the assessments after chemoradiation (Week 14) will include MRI, endoscopy and DRE and biopsy, if required. This is all based on a modification of tumor evaluation as described by [Maas 2015](#). Tumor assessments done during long-term Safety Follow-up will only include MRI (T_2 weighted and diffusion weighted) or CT scans ([Table 1](#) and [Table 2](#)).

Baseline assessments are to be taken not earlier than 4 weeks prior to study intervention start/randomization. After study intervention start/randomization, tumor assessments will be performed at 14 weeks (± 7 days) after study intervention start/randomization (i.e. before surgery) and 27 weeks (± 2 week) after study intervention start/randomization, every 3 months thereafter (± 2 weeks) until 1 year after study intervention start/randomization.

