8.1.2.2 Tumor Response Evaluation

After induction chemotherapy: Response evaluation after induction chemotherapy and restaging before study intervention with peposertib and CRT are provided in [Appendix 5](#). The evaluation with MRI, endoscopy, and DRE is to be done before starting treatment/randomization (peposertib and CRT). Overall response is evaluated as progressive disease, stable disease, partial response, nearly complete response, or complete response. Participants who present with stable disease, partial response, or nearly complete response may enter the study, participants who present with tumor progression or cCR should be treated according to standard practice per institutional guidelines.

After peposertib and CRT: Response evaluation criteria after treatment and restaging before surgery are provided in [Appendix 5](#). The evaluation with MRI, endoscopy, and DRE is to be done at Week 14 (± 7 days). Overall response is evaluated as progressive disease, incomplete response, nearly complete response, or complete response.

During Long-term Safety Follow-up: Response evaluation is provided in [Appendix 5](#).

If a scan shows progressive disease, it will be indicated whether it is local recurrence, distant recurrence, or both.

Tumor assessments are performed until progressive disease or the participant withdrawal of consent. Tumor assessments will be stopped on subsequent start of new anticancer therapy, with the exception of starting adjuvant treatment described in [Section 6.5](#).

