MRI-T2W	Increase in tumor size	
 • More intermediate than dark T2 signal, • no T2 scar AND/OR 
 • No regression of lymph nodes 	
 • Mostly dark T2 signal, • Some remaining intermediate signal AND/OR 
 • Partial regression of lymph nodes 	
 • Normal appearing bowel wall without any fibrosis in the tumor bed. • Only dark T2 signal, no intermediate T2 signal. • No visible lymph nodes or very few, small (< 5 mm nodes)

MRI=magnetic resonance imaging.

All participants, including those not undertaking surgery after chemoradiation are expected to continue loco-regional status evaluation (Table 17, MRI and optional Endoscopy/Digital), until progressive disease, at the frequency described in Section 8.1.2 and the SoA (Table 2) for Long-term Follow-up evaluations (Week 27, thereafter every 3 months in Year 1: Weeks 39 and 52).

Table 17 Response Criteria During Long-Term Safety Evaluation

Method	Progression	Complete Response
MRI-T2W or CT	
 • Local recurrence AND/ OR 
 • distant recurrence 	
 • No evidence of disease

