For identification of previous or concomitant medications/procedures, no formal imputation will be performed on missing or incomplete dates. Table 3 indicates whether a treatment is considered to be stopped before or after start of treatment. Rules presented in [Table 4](#) will be used to define if a medication/procedure is considered as a previous, concomitant or both previous and concomitant medication/procedure.

Table 3 Stopping rules for medication/procedure end dates

End date of medication/procedure			Stopping rule
Day	Month	Year	
UNK	UNK	UNK	After treatment start (ongoing)
UNK	UNK	< Treatment start (year)	Before treatment start
UNK	UNK	>= Treatment start (year)	After treatment start
		< Treatment start (month and year)	Before treatment start
		>= Treatment start (month and year)	After treatment start
		< Treatment start (complete date)	Before treatment start
		>= Treatment start (complete date)	After treatment start

UNK = Unknown

Table 4 Rules to define previous and/or concomitant medications

Start date of medication/procedure			Stopping rule (see Table 3)	Medication/ procedure
Day	Month	Year		
UNK	UNK	UNK	Before treatment start	Previous
UNK	UNK	UNK	After treatment start	Previous and concomitant
UNK	UNK	<= Treatment start (year)	Before treatment start	Previous
UNK	UNK	<= Treatment start (year)	After treatment start	Previous and concomitant
UNK	UNK	> Treatment start (year) and <= Treatment end + 30 days (year)	After treatment start	Concomitant
UNK		<= Treatment start (month and year)	Before treatment start	Previous
UNK		<= Treatment start (month and year)	After treatment start	Previous and concomitant
UNK		> Treatment start (month and year) and <= Treatment end + 30 days (month and year)	After treatment start	Concomitant
		<= Treatment start (date)	Before treatment start	Previous
		<= Treatment start (date)	After treatment start	Previous and concomitant
		> Treatment start (date) and <= Treatment end + 30 days (date)	After treatment start	Concomitant

UNK = Unknown

Tumor assessments

Tumor response assessments will be based on MRI, endoscopic and digital rectal evaluation (DRE). All investigation dates (e.g. MRI, endoscopy, DRE) must be completed with day, month and year.

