- Number of participants with a minimum of 90%, 70-90%, 50-70%, and < 50% level of the planned dose.

The listing of exposure data (including e.g. start date and time of administration, planned and actual doses, frequency, change in dose and meal time before dose) will be provided by subject as recorded from the related eCRF pages and for each peponsertib, RT and capecitabine administration.

In addition, a summary listing will be provided with the treatment duration in weeks, the total number of treatment administrations/fraction days received, the cumulative dose, and the relative dose intensity for each subject and treatment.

In addition, a listing of all participants receiving peposertib will be displayed to address accountability for peposertib according to page “peposertib/Placebo accountability” of eCRF. This listing will include the subject identification number, and all collected fields of the corresponding eCRF Page.

14 Efficacy Analyses

No primary efficacy endpoints are planned in Phase Ib of this study. Secondary efficacy endpoints include the composite endpoint of pathological complete response / clinical complete response (pCR/cCR), disease-free survival (DFS) time, pCR according to local review, cCR and time to local/distant recurrence.

In the context of efficacy analyses when using ‘surgery’, the rectal surgery at Week 15 is meant. Consequently, delayed rectal surgeries, or surgeries other than the one planned at Week 15 are not considered.

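### Local regrowth found by endoscopy, DRE or biopsy in an unoperated Week 14 cCR participant has no DFS event rule and can be censored as event-free

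*Protocol*

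**What the plan says.** **Which methods are used in follow-up.** Protocol 8.1.2 says "Tumor assessments done during long-term Safety Follow-up will only include MRI" and names CT as the alternative. The long-term schedule (Protocol Table 2) agrees: it lists MRI/CT from Week 27 and shows no endoscopy or DRE row. Appendix 5 differs. It says that all participants, "including those not undertaking surgery after chemoradiation are expected to continue loco-regional status evaluation (Table 17, MRI and optional Endoscopy/Digital), until progressive disease".

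**What counts as follow-up progression.** Table 17 in Appendix 5 is the only set of follow-up criteria. It has a single row, for MRI or CT, and lists local recurrence as progression without defining it. Protocol 8.1.2.2 also starts from imaging: "If a scan shows progressive disease, it will be indicated whether it is local recurrence, distant recurrence, or both". Tables 15 and 16, for screening and Week 14, do have endoscopy and DRE rows.

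**When assessment ends.** Under Protocol 8.1.2.2, "Tumor assessments will be stopped on subsequent start of new anticancer therapy", with adjuvant treatment excepted. SAP 9, in its rule for incomplete dates, includes surgery among subsequent anti-cancer therapies.

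**Who is unoperated.** The Surgery text in Protocol 8 allows surgery to be omitted "if the participant has a cCR and is eligible for organ preservation". Under Protocol 3.1 and SAP 14.1 such participants are responders for the pCR/cCR composite.

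**How the endpoints are built.** DFS (SAP 14.2) runs to first documented objective progression or death, and otherwise is censored at the last adequate tumor assessment. Time to local recurrence (SAP 14.3) includes only participants who had the Week 15 surgery.

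**The concern.** A participant with a cCR who keeps the rectum can fail locally in a way that is first seen or felt in the lumen. Appendix 5 permits the examinations that would find this, but the follow-up criteria give no category in which the finding is progression, and the DFS rules do not supply one. If the participant then has a salvage resection, the tumor is gone before any scan has to show it.

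The error runs in one direction. An uncounted regrowth can only raise DFS, and it does so among participants already scored as responders without surgery, so organ preservation would look more durable than it was. Two sites with the same finding could also produce an event in one case and a censoring in the other.

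**Working it through.** The documents give no DFS event count, power or target to reproduce, so the check has two parts: follow one participant through the rules, then size the effect.

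**Path of one participant**

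1. Week 14 cCR, no Week 15 surgery: a composite responder.
2. Week 27 MRI is clear. Table 17 gives complete response. The next scheduled scan is Week 39.
3. Between those scans, optional endoscopy shows regrowth and a biopsy is positive. Table 17 has no row for this, and Protocol 8.1.2.2 classifies progression from a scan.
4. Salvage resection follows. If it counts as new anticancer therapy, as the SAP 9 wording suggests, tumor assessments stop.
5. SAP Table 6: no recorded progression and no death, so DFS is censored at the last assessment without progression, here Week 27.
6. If scanning continues instead, a clear scan after resection scores complete response under Table 17, and DFS is censored at that later scan. The event is lost on either reading.
7. Time to local recurrence does not recover it, because the participant had no Week 15 surgery.

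**Size of the effect (illustration)**

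Inputs from the documents: 19 participants treated as of 06 May 2021 (Protocol synopsis); scans at Weeks 27, 39 and 52; 30.4375 days per month (SAP 9).

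Assumptions: regrowth is found at Week 33 after a clear Week 27 scan, with no further scans; 0, 2 or 4 other participants have events, split equally between Weeks 27 and 39; everyone else is followed event-free to Week 52.

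Censoring falls at 27 × 7 / 30.4375 = 6.2 months; the event would fall at 33 × 7 / 30.4375 = 7.6 months. The Kaplan-Meier estimate is the product of (1 − events / number at risk). For one regrowth:

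| Other events | Censored at Week 27 | Counted at Week 33 | Difference (points) |
|---|---|---|---|
| 0 | 100% | 18/19 = 94.7% | 5.3 |
| 2 | 18/19 × 16/17 = 89.2% | 18/19 × 17/18 × 16/17 = 84.2% | 5.0 |
| 4 | 17/19 × 14/16 = 78.3% | 17/19 × 16/17 × 14/16 = 73.7% | 4.6 |

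The same calculation gives 9.1 to 10.5 points for two such cases and 13.5 to 15.8 for three. If scanning continues to a clear Week 52, one lost event costs exactly 1/19 = 5.3 points.

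For scale, if true 1-year DFS were 80% (assumed), its standard error at n = 19 would be √(0.8 × 0.2 / 19) = 9.2 points, so one lost event is 5.3 / 9.2 = 0.57 standard errors.

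**The case against.** **The conflict is narrower than it may look.** SAP 9 says "Tumor response assessments will be based on MRI, endoscopic and digital rectal evaluation (DRE"), and a reader might infer that follow-up progression is defined in three ways. It is not. That sentence is general, names no period and is accurate for Week 14. There is one set of follow-up criteria, Table 17, and one conflict over permitted methods, between Protocol 8.1.2 with Table 2 and the Appendix 5 text. This stands. The SAP sentence still needs alignment, because the date rule that follows it lists MRI, endoscopy and DRE dates and notes that the choice of date can affect the progression date.

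**Progression could still be recorded.** A reader might infer that sites cannot enter an endoscopic regrowth as progression. The documents do not show that. SAP DFS names no method, and the follow-up listings carry assessment method and overall status. The plan neither requires nor excludes it, which leaves the outcome to the site.

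**SAP 14 is not a DFS censoring rule.** It says "delayed rectal surgeries, or surgeries other than the one planned at Week 15 are not considered", and a reader might take this as removing salvage surgery from DFS. It fixes what surgery means in the efficacy section; the DFS definition does not refer to surgery. The gap is the absence of a rule in SAP 14.2.

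**The consequence is limited.** DFS is secondary and exploratory, Phase II is cancelled, and listings of late rectal surgery, subsequent treatment and follow-up assessments would let a careful reader see a salvage case. Protocol 4.1.3 requires surgery barring contraindication or refusal and does not mention cCR, so there may be few unoperated responders, or none. Regrowth visible on a later scheduled scan before new therapy would still count. All of this stands. It limits the priority but leaves the Kaplan-Meier estimate without a stated rule.

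**Imaging on a common schedule is defensible.** Optional endoscopy makes detection depend on the site. That is a reason to report both versions. A rule counting any tumor found in any later resection would go too far: residual tumor at Week 15 is only a non-pCR, and the same finding in a merely delayed operation should not become a DFS failure.

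**Conclusion.** The concern holds as an unreconciled conflict over follow-up methods combined with a missing event rule. Local regrowth documented other than by a scan, in an unoperated Week 14 cCR participant who then has salvage resection, need not be a DFS event, and no other time-to-event endpoint captures it. The bias can only be upward, at about 5 points of 1-year DFS per case (4.6 to 5.3 in the illustration).

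The size rests on n = 19 and the assumed timings. A reader might want a probability that an event is missed, but the documents support none: they give neither the number of unoperated responders nor a regrowth rate, and the chance of a regrowth is not the chance that it goes uncounted. The dose-finding conclusions are untouched. The point should be settled before the end-of-study follow-up analysis.

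**What to change.** 1. Reconcile Protocol 8.1.2, the Appendix 5 text with Table 17, and SAP 9 on which methods may document progression during follow-up.
2. In SAP 14.2, for participants without Week 15 surgery who had a Week 14 cCR, count as progression, dated at first documentation: local regrowth documented by endoscopy/DRE or biopsy, or tumor confirmed in a later resection done for suspected regrowth. State that a resection that is merely delayed, without suspected regrowth, is not a DFS event, and that this derivation may use later rectal surgery despite the general sentence in SAP 14.
3. Report DFS with imaging-only progression as a sensitivity analysis.

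The cost is SAP wording, one derivation and one extra analysis, with no additional examination. The SAP already plans to list the eCRF page for rectal surgery after Week 15. The documents do not show whether that page holds histology or whether the date of an endoscopic finding is captured; this should be checked first. The downside is that optional endoscopy is not uniform across sites, and DFS may look slightly less favourable.

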8.1.2.1 Evaluation Methods

MRI: A standard and diffusion-weighted MRI sequences will be obtained in 1.5T or 3T units by using a phased array body coil. All images will be interpreted by expert radiology staff at the participant primary treatment center for participant eligibility, clinical staging, according to standard clinical criteria, including extramural vascular invasion and CRM assessment. For all participants, evaluation up to 28 days prior to start study intervention/randomization is allowed.

If induction chemotherapy was given, an MRI must be done to evaluate tumor changes after chemotherapy. It should be done as described above and within 2 weeks after the last day of chemotherapy but before starting study intervention/randomization.

Endoscopy with photography: Is to be done along with DRE and MRI. The length of the tumor is defined as the difference between the distance of the proximal and distal margins of the lesion in relation to the anal verge.

If participant received induction chemotherapy, endoscopy will be performed 2 weeks (± 14 days) after the last day of chemotherapy but before starting study intervention/randomization to evaluate tumor changes after chemotherapy.

Digital Rectal Exam: If the tumor cannot be reached on digital rectal exam, this should be noted on the checklist and evaluation. The digital rectal exam criteria are applicable to participants with palpable tumor only.

In case induction chemotherapy was given, a DRE must be done to evaluate tumor changes after chemotherapy. It should be done within 2 weeks (± 14 days) after the last day of chemotherapy but before starting study intervention/randomization.

Biopsy: Only to be done during the endoscopy if required and as per institutional guidelines.

8.1.2.2 Tumor Response Evaluation

After induction chemotherapy: Response evaluation after induction chemotherapy and restaging before study intervention with peposertib and CRT are provided in [Appendix 5](#). The evaluation with MRI, endoscopy, and DRE is to be done before starting treatment/randomization (peposertib and CRT). Overall response is evaluated as progressive disease, stable disease, partial response, nearly complete response, or complete response. Participants who present with stable disease, partial response, or nearly complete response may enter the study, participants who present with tumor progression or cCR should be treated according to standard practice per institutional guidelines.

After peposertib and CRT: Response evaluation criteria after treatment and restaging before surgery are provided in [Appendix 5](#). The evaluation with MRI, endoscopy, and DRE is to be done at Week 14 (± 7 days). Overall response is evaluated as progressive disease, incomplete response, nearly complete response, or complete response.

During Long-term Safety Follow-up: Response evaluation is provided in [Appendix 5](#).

If a scan shows progressive disease, it will be indicated whether it is local recurrence, distant recurrence, or both.

Tumor assessments are performed until progressive disease or the participant withdrawal of consent. Tumor assessments will be stopped on subsequent start of new anticancer therapy, with the exception of starting adjuvant treatment described in [Section 6.5](#).

8.1.2.3 Neoadjuvant Rectal Score

The neoadjuvant rectal score (NAR) was developed by George and colleagues to serve as a short term clinical study surrogate endpoint ([George 2015](#)). The Valentini nomograms ([Valentini 2011](#)) to predict overall survival in rectal cancer patients after neoadjuvant treatment are the basis of the NAR score. Its score ranges from 0 to 100, whereas a score close to 100 is indicative of a poorer prognosis.

The NAR formula includes the clinical tumor (cT) stage, pathologic tumor (pT), and node (pN) stage according to the tumor, node, metastasis classification system for colorectal cancers. The NAR formula is as follows:

$$\text{NAR} = \frac{[5pN - 3(cT - pT) + 12]^2}{9.61}$$

8.2 Safety Assessments and Procedures

The safety profile of the study intervention will be assessed through the recording, reporting and analysis of baseline medical conditions, AEs, physical examination findings, vital signs, and laboratory tests.

The safety observation is divided into the following periods:

- **Baseline:** safety evaluation before the initiation of study intervention
- **Treatment Period:** during study intervention
- **Short-term Safety Follow-up:** evaluations after the Treatment Period, including the perioperative and postoperative observation (until Week 19)
- **Long-term Safety Follow-up:** up to 1 year.

Participants who have already been followed up for more than 1 year (Long-term Safety or Survival Follow-up) will be discontinued from the study after the approval of protocol amendment version 4.0 by the respective Health Authority and Ethics Boards.

Frequency of visits and specific procedures are described in [Table 1](#) and [Table 2](#).

Comprehensive assessment of any potential toxicity experienced by each participant will be conducted starting when the participants give informed consent and throughout the study. The Investigator will report any AEs, whether observed by the Investigator or reported by the participant; the reporting period is specified in Section 8.3.1 (Time Period and Frequency for Collecting Adverse Event and Serious Adverse Event Information).

8.2.1 Physical Examinations

A complete physical examination will be performed at Screening and a brief physical examination will be performed at all other time points indicated in the SoA (Section 1.3).

- A complete physical examination will include, at a minimum, assessments of the Cardiovascular, Respiratory, Gastrointestinal, and Neurological systems. Height (at Screening) and weight will also be measured and recorded.
- A brief physical examination will include, at a minimum, assessments of the skin, lungs, cardiovascular system, and abdomen.
- Investigators should pay special attention to clinical signs related to previous serious illnesses.
- Investigators will report findings in the irradiated area during the Short- and Long-term Safety Follow-up periods.

For participants with a change in body weight of at least 10% from baseline, individual capecitabine doses should be recalculated. See Section 6.1 for details.

8.2.2 Vital Signs

- Temperature, pulse rate, respiratory rate, and blood pressure will be assessed.
- Blood pressure and pulse measurements will be assessed in a semi-supine position with a completely automated device. Manual techniques will be used only if an automated device is not available.
- Blood pressure and pulse measurements should be preceded by at least 5 min of rest for the participant in a quiet setting without distractions (e.g. television, cell phones).
- Vital signs (to be taken before blood collection for laboratory tests) will consist of 1 pulse and 3 blood pressure measurements (3 consecutive blood pressure readings will be recorded at intervals of at least 1 min). The average of the 3 blood pressure readings will be recorded on the CRF.

